6.2.2 Objective 1 Secondary Analyses

We will use regression methods to assess the impact of the telehealth intervention on secondary outcomes of telehealth visit completion, rate of comprehensive molecular testing, patient satisfaction, clinician acceptability, and intervention costs, with logistic, Cox proportional hazards, and linear regression for binary, time-to-event, and continuous outcomes, respectively. Additional secondary analyses will adjust for factors that exhibit residual imbalance between randomized intervention groups. In addition, secondary as-treated analyses will be conducted.

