Interventions	Eligible patients will be individually randomized to one of two arms: 
 1. Usual care – standard nurse navigation. 2. Enhanced nurse navigation – synchronous telehealth nurse navigation visit prior to biopsy.
Outcomes	
Objective 1: Receipt of a molecularly-informed treatment recommendation for patients with metastatic NSq NSCLC at the time of the patient's initial oncology visit.
 
Secondary Outcomes:
 
 1. Rate of telehealth visit completion 2. Rate of completion of comprehensive molecular testing (tissue and/or plasma testing) prior to initiation of first line therapy 3. Identification of one or more targetable mutations 4. Timeliness of molecularly-informed treatment recommendation 5. Overall survival 6. Intervention costs 7. Proportion of patients with diagnosis other than metastatic nonsquamous NSCLC (Telehealth arm only) 8. Time to treatment initiation 
Objective 2: Individual and contextual factors (e.g., treatment knowledge, medical mistrust, clinical beliefs, organizational climate, patient-centered communication, financial toxicity, and knowledge of genetic testing) shaping trial effectiveness and patient experience.

Primary Analysis	
Objective 1: Intention-to-treat (ITT) analyses for effectiveness using logistic regression.
 
Objective 2: Mixed methods evaluation of descriptive survey data and thematically coded interview data.

Study Oversight	[name] (PI) will be responsible for monitoring the trial and ensuring subject safety, as well as the integrity of the interventions and the data collected. Trial oversight will be conducted by the University of Pennsylvania Institutional Review Board.

Contents

Principal Investigator:	1
Funding Agency:	1
Protocol Summary	2
1. BACKGROUND AND RATIONALE	5
2. OBJECTIVES	6
2.1 Primary Objectives	6
2.2 Primary Outcomes	6
2.3 Secondary Outcomes	6
3. STUDY POPULATION	6
3.1 Target Population	6
3.2 Inclusion Criteria	6
4. STUDY DESIGN	7
4.1 Preliminary Studies	7
4.2 Overview	7
4.3 Study Duration and Timeline	10
4.4 Study Setting	10
5. STUDY PROCEDURES	11
5.1 Recruitment and Retention	11
5.2 Informed Consent	11
5.3 Compensation	12
5.4 Measures and Endpoints	13
5.5 Sources of Materials	14
6. STATISTICAL DESIGN AND POWER	14
6.1 Sample Size	14
6.2 Analysis Plan	14
6.2.1 Objective 1 Primary Analyses	14
6.2.2 Objective 1 Secondary Analyses	15
6.2.3 Objective 1 Exploratory Analyses	15
6.2.4 Objective 2 Analyses	15

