2.3 Secondary Outcomes

Objective 1: Secondary outcomes include:

- 1) Rate of telehealth visit completion
- 2) Rate of completion of comprehensive molecular testing (tissue and/or plasma testing) prior to initiation of first line therapy
- 3) Identification of one or more targetable mutations
- 4) Timeliness of molecularly-informed treatment recommendation
- 5) Overall survival
- 6) Intervention costs
- 7) Proportion of patients with diagnosis other than metastatic NSq NSCLC (telehealth arm only)
- 8) Time to treatment initiation

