4.2 Overview

Prior to the trial launch, we will use a rapid-cycle approach (RCA) to optimize delivery of the enhanced synchronous telehealth nurse navigation visit and coordination/default ordering of molecular testing. RCA procedures will involve design meetings with the study team, discussions with administrators and clinicians who are members of our Implementation Lab, as well as contextual inquiry with clinicians and patients to elicit feedback.

Objective 1: As shown in **Figure 1**, this two-arm pilot trial will randomize patients with suspected locally advanced/metastatic NSCLC who are scheduled for an appointment in the lung cancer evaluation clinic. Eligible patients will be identified by screening of clinical schedules by study staff using the EMR. Prior to or soon after completing an appointment in the lung cancer evaluation clinic, eligible patients will be randomized to either enhanced synchronous telehealth nurse navigation or to usual care nurse navigation.

Usual Care Arm:

Currently, in the standard care pathway at Penn Medicine, a patient who is being evaluated for lung cancer has an appointment within the lung cancer evaluation clinic and is then scheduled for a biopsy (e.g., bronchoscopy, transthoracic needle biopsy). After the biopsy is complete, the patient's clinician contacts the trained lung cancer nurse navigator, who then calls the patient to 1) review the roles of clinicians on the medical oncology care team; 2) provide brief education on lung cancer; and 3) review the patient's diagnostic history and coordinate collection or completion of imaging required for guideline-recommended cancer staging. In the standard care pathway at Penn Medicine this phone call between the patient and the lung cancer nurse navigator usually takes place after the biopsy is complete, though there are some cases in which the clinician asks the lung cancer nurse navigator to reach out to the patient sooner.

For patients randomized to the usual care arm of this study, the researchers will ask the clinicians and the lung cancer nurse navigator not to arrange plasma-based testing earlier than the date of the initial in-person medical oncology visit. Instead, the lung cancer nurse navigator can have the patient complete a blood draw for plasma-based testing on the same day as their initial in-person medical oncology visit.

Intervention (Telehealth) Arm:

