Patients in the intervention arm will be scheduled for an enhanced synchronous telehealth visit with a trained lung cancer nurse navigator prior to tissue biopsy. The enhanced synchronous telehealth visit will ideally occur between the initial clinical appointment and diagnostic biopsy (typically a period between two and seven days). In addition to the activities conducted as part of usual care, the nurse navigator will: 1) provide more detailed and individualized education on lung cancer and the rationale for comprehensive molecular testing, including plasma-based tests; and 2) if the patient agrees to testing, pend a default order for plasma-based molecular testing (if not already ordered) for the clinician to sign and arrange for phlebotomy to be performed during the periprocedural window associated with the patient's tissue biopsy.

Objective 2: Using rigorous approaches proven successful in our prior work,^{15,16} we will recruit 20-30 patient participants of the primary trial and 10-15 clinicians and clinical leaders to complete semi-structured interviews following the active trial period.

Patients: We will oversample for Black patients to understand effectiveness by race/ethnicity and stratify by trial outcome and study arm to understand factors contributing to both success and failure (e.g., primary endpoint) in either group (5-10 patient in each stratum). Trial participants will be invited in randomly selected batches each month (to enhance capture over time) until we reach our target sample of approximately 20-30 patients. Patients will be invited to participate in interviews via email and/or letter within 6 weeks of their in-person oncology visit.

Clinicians: Recruitment for clinicians will be similar to the procedure for patients, except we will wait until the completion of the full trial to conduct interviews to avoid potential contamination. Clinicians will be purposively sampled by clinical role (e.g., oncologists, nurses, clinical leads) to enhance variation and invited via email. Recruitment will continue until we reach our target sample of 10-15 clinicians.

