5. STUDY PROCEDURES

5.1 Recruitment and Retention

Objective 1: This study will employ a waiver of consent mechanism (see Section 5.2 Informed Consent). Eligible patients will be identified from weekly screening of appointments scheduled at the lung cancer evaluation clinic at Penn Medicine. The process will be optimized to identify all patients with suspected locally advanced/metastatic NSCLC. After eligibility is confirmed based on review of medical records, eligible participants will be randomized to receive an early enhanced synchronous telehealth nurse navigation visit (intervention) or standard nurse navigation (usual care). After completion of the initial clinical appointment, patients in the telehealth arm will be scheduled to receive a synchronous visit (with audio and video capabilities) with a lung cancer trained nurse navigator prior to their tissue biopsy.

Objective 2: This portion of the study will utilize prospective consent with waiver of written documentation (see Section 5.2 Informed Consent). An estimated 20-30 patients and 10-15 clinicians and clinical leaders will be interviewed (sample size dependent upon when data saturation is reached). Interview participants will also complete a survey before or at the time of the interview.

Patients: A sample of patients enrolled in the randomized clinical trial will be invited to participate in the semi-structured interview and survey via email or letter within 6 weeks of in-person visit. Participants will be invited in randomly selected batches (estimate approximately 5 per month to enhance capture over time) until we reach our target sample of approximately 20-30 patients. We will oversample for Black patients to understand effectiveness by race/ethnicity and stratify by trial outcome (treatment recommendation or not) and study arm (telehealth versus usual care) to understand factors contributing to both success and failure of the telehealth strategy (5-10 patients in each stratum).

Clinicians: Recruitment of clinicians will be similar to that of patients, except we will wait until the completion of the full trial to conduct interviews to avoid potential contamination. Clinicians will be randomly selected and invited via email. Recruitment will continue until we reach our target sample of 10-15 clinicians, purposively sampled by role (oncologists, nurses and advanced practice providers, practice managers, and health system leaders).

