5.4 Measures and Endpoints

Objective 1: The specific outcomes align with 5 key endpoints (access, quality, outcomes, equity, and efficiency). The primary endpoint is receipt of a molecularly-informed treatment recommendation at the time of the patient's initial in-person oncology visit, measured up to 12 weeks from randomization. This outcome encompasses successful completion of comprehensive molecular testing and the ability of the patient and oncology care team to have all necessary information to collaboratively arrive at the optimal treatment approach. We anticipate that approximately 10% of patients randomized to usual care will be able to receive a molecularly-informed treatment recommendation at initial visit – these include patients in whom tissue was successfully tested and identified a targetable mutation prior to referral. We anticipate this will be substantially improved with enhanced nurse navigation (See Section 6.1 Sample Size). The primary endpoint will be assessed by review of clinician documentation (e.g., progress notes) within the electronic medical record (EMR) on the day of the initial visit.

Secondary outcomes include:

- 1) Operational endpoints:
 - a. Rate of completion of telehealth visit defined as successful completion of a nurse navigator telehealth visit prior to biopsy, measured up to 3 weeks from randomization.
 - b. Rate of completion of comprehensive molecular testing (tissue and/or plasma testing) prior to initiation of first line therapy, measured up to 12 weeks from randomization.
- 2) Clinical endpoints:
 - a. Time from randomization to molecularly-informed treatment recommendation, measured up to 12 weeks from randomization.
 - b. Proportion of participants with one or more targetable mutations, measured up to 12 weeks from randomization.
 - c. Overall survival, measured as 1-year overall survival from time of randomization to death from any cause.
 - d. The proportion of enrolled patients with a diagnosis other than metastatic NSq NSCLC (telehealth arm only), measured at 12 weeks from randomization.
 - e. Time from randomization to treatment initiation, measured up to 12 weeks from randomization.
- 3) Cost outcomes:
 - a. Intervention costs (measured using a pragmatic method to capture and analyze all system-level resources, such as personnel time and patient outreach costs) that are needed to deploy telehealth strategies in routine care.¹⁹

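### Section 6.2.2 plans between-arm regressions for telehealth visit completion and clinician acceptability, for which the described design gives no meaningful arm contrast

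*Combined protocol and SAP*

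**What the plan says.** The analysis sentence in Section 6.2.2 reads "We will use regression methods to assess the impact of the telehealth intervention on secondary outcomes of telehealth visit completion" and then adds the molecular testing rate and "patient satisfaction, clinician acceptability, and intervention costs". It assigns logistic, Cox or linear regression according to outcome type.

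On visit completion, Section 5.4 defines the outcome as "successful completion of a nurse navigator telehealth visit prior to biopsy". Section 4.2 says who is offered that visit: "Patients in the intervention arm will be scheduled for an enhanced synchronous telehealth visit with a trained lung cancer nurse navigator". Section 5.1 repeats this for the telehealth arm and describes a visit with sound and picture. For usual care, Section 4.2 describes a telephone call and says "this phone call between the patient and the lung cancer nurse navigator usually takes place after the biopsy is complete", while allowing that a clinician sometimes asks for earlier contact.

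On clinicians, the Protocol Summary makes the patient the unit of allocation: "Eligible patients will be individually randomized to one of two arms". Section 5.1 plans to interview 10-15 clinicians, sampled by role, once the full trial is complete, with a survey at or before the interview.

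On surveys generally, Section 6.2.4 plans a descriptive analysis.

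The plan already restricts one secondary outcome to a single arm in Section 2.3: "Proportion of patients with diagnosis other than metastatic NSq NSCLC (telehealth arm only".

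**The concern.** A regression on arm needs an outcome that both arms could show, measured on units that have an arm. Visit completion fails the first condition, because it records delivery of the assigned intervention. Clinician acceptability fails the second, because clinicians are not allocated and no section describes them rating individual patients' care by arm.

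Followed as written, 6.2.2 would give a model that does not converge, or an odds ratio that says only that the visit went to those assigned to it, and a second model that cannot be run. An analyst would then have to choose replacements after seeing the data. Section 6.1 says the outcomes are to inform later studies, and for that purpose the useful figure is a completion proportion with its precision.

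There is also an inconsistency. Section 6.2.2 calls patient satisfaction and clinician acceptability secondary outcomes, but neither is on the lists in the Protocol Summary, Section 2.3 or Section 5.4.

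**Working it through.** **Inputs.** From Section 6.1: 69 patients per arm, 10% primary-outcome success in usual care and an absolute increase of 20 points, so 30% with telehealth. From Section 5.1: 10-15 clinicians, and 20-30 interviewed patients with 5-10 per stratum. The documents give no visit completion rate, so the range 41, 55 or 62 of 69 (about 60-90%) is an assumption.

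**The plan's own figure.** The documents give no power or precision for the outcomes at issue. The 69 per arm used as denominator does reproduce. With two-sided alpha of 0.05 (assumed, as the value is not stated) and pooled proportion 0.20:

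n = [1.96 × √(2 × 0.2 × 0.8) + 0.842 × √(0.1 × 0.9 + 0.3 × 0.7)]² / 0.20² = (1.109 + 0.461)² / 0.04 ≈ 61.6, so 62 per arm and 124 in total. Then 124 / 0.9 = 137.8, so 138.

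**1. Visit completion, no usual-care completions.** The odds ratio is ad/(bc), where a and b are telehealth completed and not completed, and c and d are the same for usual care. With c = 0 the denominator is zero and the maximum likelihood estimate is infinite.
- At 48/69 against 0/69, the fitted log odds ratio moved from 12.0 (SE 33) to 17.2 (SE 439) to 21.6 (SE 3,952) as the iteration limit rose from 10 to 25 to 35.
- Binomial fits at 41, 55 and 62 of 69 stopped at coefficients 24.9, 25.9 and 26.7, each with SE about 15,772 and Wald p = 0.999. These are signs of separation, not estimates.

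**2. Visit completion, a few early usual-care contacts counted.** SE(log OR) = √(1/a + 1/b + 1/c + 1/d).
- 55/69 against 1/69: OR = (55 × 68)/(14 × 1) = 267; SE = √(1/55 + 1/14 + 1/1 + 1/68) = 1.051; 95% CI 34 to 2,095.
- 55/69 against 5/69: OR = (55 × 64)/(14 × 5) = 50; SE = √(1/55 + 1/14 + 1/5 + 1/64) = 0.552; 95% CI 17 to 148.

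The model now fits, but the estimate swings about fivefold on four patients and describes who was scheduled.

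**3. Visit completion, telehealth arm alone** (exact Clopper-Pearson 95% CI):

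| Completed | Proportion | 95% CI |
|---|---|---|
| 41/69 | 59% | 47-71% |
| 55/69 | 80% | 68-88% |
| 62/69 | 90% | 80-96% |

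**4. Clinician acceptability.** There is no arm variable for a clinician, so the design matrix has no arm column and there is nothing to estimate. A descriptive mean has 95% half-width t(0.975, n-1)/√n in SD units: 2.262/√10 = 0.72 SD for n = 10, and 2.145/√15 = 0.55 SD for n = 15.

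**5. Patient satisfaction, only if compared within the interview subset.** That subset is stratified by primary outcome and arm. Suppose satisfaction differs by d between success and failure (d is not in the documents) and arm has no other effect. The true arm difference is then (0.30 - 0.10)d = 0.20d, whereas equal strata without weights give (0.50 - 0.50)d = 0. Weighting removes this. With k patients per stratum and within-stratum SD of 1, the weighted SE is √[(0.1² + 0.9² + 0.3² + 0.7²)/k] = √(1.40/k), which is 0.53 for k = 5 and 0.45 for k = 7. The 95% half-widths are 1.04 and 0.88 SD. For d of 0.25 to 1.0 SD the bias is 0.05 to 0.20 SD, so small numbers are the larger problem.

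**The case against.** The best reply is that this is a pilot and nobody would be misled by an odds ratio for receiving the visit one was assigned. Delivery by arm is a legitimate check on adherence and contamination, and the early contacts allowed in Section 4.2 might make the model estimable. This stands in part. The non-finite result depends on a usual-care count of exactly zero, and early contacts are worth reporting. A proportion in one arm and a count in the other serve that purpose better than a regression coefficient.

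It can also be said that Section 6.2.4 already treats survey data descriptively. That is true, but it means 6.2.2 and 6.2.4 disagree and one must change.

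On satisfaction, a reader might infer that the plan commits itself to an unweighted arm regression in the outcome-sampled interviewees and so to a biased result. The documents do not support that. Section 6.2.2 names neither the sample nor the weighting. Section 5.5 mentions survey data for secondary endpoints and quantitative measures within the randomised trial, and Section 5.2 lists satisfaction among key outcomes. No section describes a survey of all 138 patients, but none rules it out. Nor do the documents say whether usual-care patients would answer the telehealth usability questionnaire, the one instrument named for satisfaction in Section 5.4.

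**Conclusion.** The point holds for visit completion and clinician acceptability. For completion, the odds ratio is non-finite at 0/69 in usual care, and at one to five counted contacts it is an uninformative 267 to 50 (with 55/69 assumed in telehealth). For clinicians no arm coefficient exists at any sample size. This rests on the design as described: the visit is scheduled in one arm only, and clinicians are neither allocated nor asked for patient-level ratings.

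For patient satisfaction the documents support only a request for clarification. It would be too strong to call that comparison invalid, because an arm contrast is possible with trial-wide collection or with sampling weights. The primary endpoint and the sample size are untouched.

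**What to change.** 1. In Section 6.2.2, take telehealth visit completion out of the regressions. Report it for the telehealth arm only, as a proportion of all patients randomised to that arm with an exact 95% confidence interval, using the one-arm label already present in Section 2.3. Give early usual-care navigator contacts as a count.
2. Remove clinician acceptability from the 6.2.2 regressions and report it descriptively under Section 6.2.4, naming the instrument and who completes it.
3. Reconcile Section 6.2.2 with Sections 6.2.4, 5.2 and 5.5 on patient satisfaction: state who is surveyed, with what instrument, and whether usual-care patients complete it. Either add satisfaction and acceptability to the secondary-outcome lists or stop calling them secondary outcomes. If satisfaction is compared by arm within the interview subset, weight by sampling fraction, show the confidence interval, and note that opt-out and non-response may leave bias.

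The first two changes need no new data and leave the primary analysis alone. The cost is that two arm comparisons, or three if satisfaction proves to be measured only in the interviewees and is not compared with weights, become descriptive. The satisfaction hypothesis in Section 1 and the consent-waiver text in Section 5.2 may then need matching wording.

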6.2.3 Objective 1 Exploratory Analyses

[figure not shown]
A difference in effectiveness of the telehealth intervention for Black versus White patients will be conducted by adding a main effect of race and the interaction of race and intervention to the primary unadjusted logistic regression model. Given that hypothesis tests of interaction terms are likely severely underpowered at our pilot study sample size, we will focus statistical inference on the point estimate and 95% confidence intervals for the interaction term. While these intervals may cross the null value consistent with no difference in effectiveness, confidence intervals that largely lie away from the null provide evidence in favor of differential intervention effects that could be detected statistically with a larger sample size in a subsequent study. Patients who do not identify as Black or White will be excluded from this analysis.

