6. STATISTICAL DESIGN AND POWER

6.1 Sample Size

Objective 1: Sample size is based on estimates of receiving a molecularly-informed treatment recommendation at the initial oncology visit. Based on our prior studies, we anticipate this will occur in 10% of patients in the usual care arm. This pilot study is designed to detect an absolute increase of 20% in our primary outcome for patients in the intervention arm. With a sample size of 124 participants and a two-sided alpha, we will have >80% power to detect an increase of this magnitude. Given the potential for drop-out of patients following randomization, we have increased the estimate by 10%, leading to a final sample size of 138 participants (69 in each arm). Although a difference <20% in our primary outcome rate may be clinically meaningful, this sample size is an optimal balance to allow an assessment of our primary and secondary outcomes and assess for mechanisms of action. Study outcomes will be used to preliminarily assess effectiveness across all outcome domains to inform the design of future studies, including a pragmatic trial, if warranted.

Objective 2: Proposed sample size is based on the estimated number of interviews needed to reach data saturation within each group and by intervention outcome to support mixed methods evaluation; however, interviews will continue until saturation is achieved.^{16,21}

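### The exploratory race-by-arm comparison uses ordinary logistic regression with one cell expected to hold only about 1-3 events, and has no method for an empty cell

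*Combined protocol and SAP*

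**What the plan says.** Section 6.2.3 (Objective 1 Exploratory Analyses) examines whether the intervention works differently in Black and White patients by "adding a main effect of race and the interaction of race and intervention to the primary unadjusted logistic regression model". Patients of other races are left out. The section concedes that "hypothesis tests of interaction terms are likely severely underpowered at our pilot study sample size", and for that reason "we will focus statistical inference on the point estimate and 95% confidence intervals for the interaction term". It then gives a reading rule: an interval may cross the null, but one lying mostly to one side of it counts in favour of a differential effect that a larger study could detect.

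Section 6.1 supplies the planning rates. For the primary outcome, "we anticipate this will occur in 10% of patients in the usual care arm", and the trial is "designed to detect an absolute increase of 20% in our primary outcome", so 30% is expected under telehealth. The final size is 138, with 69 per arm.

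The documents do not state the type of interval, any penalised or exact method, a rule for an empty cell, or the expected number of Black patients. They describe no stratification by race and no enrolment target by race for the randomised sample. The oversampling of Black patients in sections 4.2 and 5.1 concerns the Objective 2 interviews.

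**The concern.** Arm, race and their product make a saturated model with four cells. The fitted interaction is the log odds ratio in Black patients minus the log odds ratio in White patients. If one cell has no events, one of those log odds ratios is infinite, and so is the interaction. Software then prints an arbitrary large number with an enormous standard error.

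This differs from low power. Low power gives a wide but valid interval, and the plan's answer to low power is to rely on the estimate and interval. Those are the two quantities that fail when a cell is empty. The reading rule adds to the problem, because an interval with no limit on one side can be described as lying mostly away from the null when its shape comes from a single empty cell. Equity is one of the five endpoint domains in section 5.4, and this is the only prespecified quantitative comparison of the effect by race.

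**Working it through.** **Planning figure.** Inputs are 10% v 30%, two-sided, and more than 80% power (section 6.1). The alpha level is not stated; 0.05 is assumed.

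n per arm = [1.960·√(2·0.2·0.8) + 0.842·√(0.1·0.9 + 0.3·0.7)]² / 0.2² = (1.109 + 0.461)² / 0.04 ≈ 61.6, so 62 per arm and 124 in total. Power at 62 per arm is 80.3%. Allowing for drop-out, 124 / 0.9 = 137.8, so 138. The plan's figures reproduce.

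**Expected events and chance of a non-finite estimate.** Take 69 per arm, 10% v 30% in both races and no other-race exclusions. The Black share is an assumption. Expected events are cell size × rate. The chance that the Black usual-care cell is empty is 0.9ⁿ. The chance that the interaction is non-finite is 1 − ∏[1 − (1−p)ⁿ − pⁿ] over the four cells.

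| Black share (n per arm) | Black usual care | Black telehealth | White usual care | White telehealth | Black usual care empty | Non-finite |
|---|---|---|---|---|---|---|
| 10% (7) | 0.7 | 2.1 | 6.2 | 18.6 | 48% | 52% |
| 15% (10) | 1.0 | 3.0 | 5.9 | 17.7 | 35% | 37% |
| 20% (14) | 1.4 | 4.2 | 5.5 | 16.5 | 23% | 24% |
| 25% (17) | 1.7 | 5.1 | 5.2 | 15.6 | 17% | 17% |
| 30% (21) | 2.1 | 6.3 | 4.8 | 14.4 | 11% | 12% |
| 40% (28) | 2.8 | 8.4 | 4.1 | 12.3 | 5% | 6% |

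Nearly all of the risk comes from the Black usual-care cell.

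**Sensitivity.**
- With 124 evaluable patients, the chance is 41% at a 15% share, 30% at 20%, 15% at 30% and 9% at 40%.
- If telehealth has no effect in Black patients (10% in both arms), two cells are at risk. At a 20% share: 1 − (1 − 0.229)² × 0.997 ≈ 41%. Simulation with race drawn at random gives 44%.

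**Worked example (25% share).** Suppose events are 0/17 v 5/17 in Black patients and 6/52 v 16/52 in White patients, close to expectation apart from the empty cell.
- Ordinary maximum likelihood: the ratio of odds ratios is infinite. Profiling the likelihood, the deviance at no interaction is 2.82 (p about 0.09). It reaches the 3.84 cut-off at a log ratio of −0.43, so the 95% interval is about 0.65 to infinity.
- Firth: in a saturated model this equals adding 0.5 to every event and non-event count. The log ratio is ln(5.5/12.5) − ln(0.5/17.5) − [ln(16.5/36.5) − ln(6.5/46.5)] = 2.73 − 1.17 = 1.56, a ratio of 4.8. The penalised profile 95% interval is about 0.36 to 690.

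**The case against.** The analysis is labelled exploratory, in a pilot meant to inform later studies, and the plan already admits that it is underpowered. A runaway estimate is plain to any analyst, and switching to a penalised or exact method is routine. Firth does not rescue the information either: in the example its interval still lies mostly on one side of the null. Exact or Bayesian methods, or risk differences within each race, would also serve. All of this stands, and it keeps the priority low. It does not remove the case for naming a method in advance, since a choice made after an empty cell has been seen is open to challenge.

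Three stronger readings are tempting, and the documents do not support them.
- A reader might infer that the model is sparse throughout. Only the Black usual-care cell is expected to hold about 1-3 events.
- A reader might infer that the estimate will usually fail. That depends on a Black share the documents do not give. From a 20% share upward, the estimate is finite in more than three-quarters of trials under the planning rates with 69 per arm.
- A reader might infer that an empty cell would pass for strong evidence of a racial difference. In the example the interval covers 1, and section 6.2.3 treats such signals only as leads for a larger study.

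**Conclusion.** The point holds as a limited defect in an exploratory analysis. For a Black share of 15-40% of 138, the specified estimator has roughly a 6-37% chance of giving no finite interaction, about 24% at a 20% share. The risk is higher with drop-out or with no benefit in Black patients. When this happens, neither the estimate nor the usual interval can be read as section 6.2.3 intends, and its reading rule could be triggered by one empty cell. The figures rest on the plan's 10% and 30% rates applying in both races, equal arms, no exclusions for other race, and an assumed Black share. The primary comparison does not depend on any of this.

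**What to change.** In section 6.2.3, replace the ordinary fit for the race-by-arm model with Firth penalised logistic regression and penalised profile-likelihood 95% intervals. State that the event count and denominator of each of the four arm-by-race cells will be reported beside the interaction estimate. The counts matter as much as the method: Firth gives a finite answer, but the counts show the reader when that answer rests on an empty or nearly empty cell.

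The cost is one sentence in the analysis plan, standard software, and slight shrinkage of the estimate towards no interaction. Sample size, data collection and the primary analysis do not change.
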